6.5 Definitions of Dose Limiting Toxicity

Reference should be made to the CTCAE, Version 4.03 for grading of the severity of adverse events and laboratory abnormalities. A DLT will be defined as any of the following adverse events that is considered by the investigator as related to RX-0201:

- Grade 4 neutropenia ($ANC < 0.5 \times 10^9/L$) with fever or lasting 3 days or longer
- Any Grade 4 thrombocytopenia or Grade 3 thrombocytopenia associated with \geq Grade 1 hemorrhage
- Any \geq Grade 3 coagulation abnormality (defined by PT and/or INR and PTT values) associated with clinical hemorrhage \geq Grade 1.
- Nausea/vomiting \geq Grade 3 despite maximal antiemetic therapy; diarrhea \geq Grade 3 despite maximal anti-diarrheal therapy.
- Grade 4 thrombocytopenia (platelet count $< 25 \times 10^9/L$)
- Any other non-hematological toxicity \geq Grade 3 with the exception of alopecia

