2.3.2 Prior Clinical Experience

In a phase 1 single agent dose escalation study of RX-0201, doses ranging from 6.0 to 315 mg/m²/day were administered to 17 subjects with solid tumors. The maximum tolerated dose of single agent administration was 250 mg/m²/day. Fatigue was the most commonly reported adverse event in 82% of subjects (14/17). Arthralgia (joint pain) and nausea were the second most commonly reported adverse events with 47% (8/17) and 35% (6/17) of subjects reporting these events, respectively. Fatigue was also the most frequently reported adverse event determined by the investigator to be related to RX-0201, with 70.6% (12/17) of subjects reporting the event, 29.4% (5/17) of the subjects reported a mild fatigue, 23.5% (4/17) of subjects reported a moderate fatigue, and 17.6% (3/17) subjects reported a severe fatigue.

A Phase 2 study of RX-0201 and gemcitabine in metastatic pancreatic cancer has been completed. In Stage 1 of this study, 11 subjects were enrolled and received gemcitabine at 1000 mg/m² for 30 minutes followed by a continuous infusion of RX-0201 at a dose of 200 mg/m²/day for 14 days. In Stage 2 of this study, 20 additional subjects were treated with gemcitabine at 1000 mg/m² for 30 minutes followed by 200 mg/m²/day of RX-0201. The most commonly reported treatment emergent adverse events related to RX-0201 were thrombocytopenia (8.7%), decreased platelet count (7.7%), neutropenia (6.7%), fatigue (5.8%), and decreased hemoglobin (5.8%).

The Phase 1b portion of this study has been completed. Seven males and 3 females, (median age 61 years) were treated with 125 mg/m²/day (n=3), 200 mg/m²/day (n=4), and 250 mg/m²/day (n=3) RX-0201 in combination with 10 mg everolimus. The most common toxicities attributed to the combination were rash, mouth ulceration, weight loss, thrombocytopenia, facial edema,

fatigue, and pruritus. No significant events were attributed to RX-0201 alone. Most events (81%) were mild or moderate in severity. Based on the tolerability, 250 mg/m²/day RX-0201 dose was declared the recommended Phase 2 dose.

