5.4 Subject Replacement

Subjects in Stage 1 who are enrolled but not treated and subjects who discontinue treatment before completion of Cycle 1 for reasons other than the occurrence of a DLT may be replaced. Any replacement subject will be enrolled into the same dosing group as that for the subject who withdrew.

Subjects in Stage 2 who are enrolled but not treated will be replaced.

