6.3 RX-0201 Dose Limiting Toxicity

Initially 3 subjects will be enrolled to receive everolimus plus 125 mg/m²/day of RX-0201. If there are any dose limiting toxicities (DLTs) attributed to RX-0201 the following dose-escalation decisions will be followed:

Table 1: Phase 1 RX-0201 Dose Escalation		
Dose Group	Theoretical dose(mg/m²/day)	Escalation
1	125	-
2	200	1.60
3	250	1.25

The following dose-escalation rules will be employed:

- If 0 of the first 3 subjects experience DLT during the first 3 weeks of treatment, then the dose will be escalated to the next higher level in 3 subsequent subjects.
- If 1 of the first 3 subjects experiences DLT at the current dose during the first 3 weeks of treatment, then 3 more subjects will be accrued at the same dose level.
- If 0 of the 3 additional subjects experience DLT during the first 3 weeks of treatment, then the dose will be escalated to the next higher level in 3 subsequent subjects.
- If ≥ 1 of the 3 additional subjects in a cohort experiences DLT in the first 3 weeks of treatment, the MTD has been exceeded and 3 more subjects will be treated at the next lower dose level (if only 3 subjects were previously treated at that prior dose level).
- If ≥ 2 of 3 or ≥ 2 of 6 subjects experience DLT during the first 3 weeks of treatment, then the MTD has been exceeded and 3 more subjects will be treated at the next lower dose level (if only 3 subjects were previously treated at that prior dose level).
- Each group of 3 subjects within a cohort must be observed for a minimum period of 3 weeks without DLT before subsequent subjects are enrolled at the next higher dose level.
- Escalation to the next dose level of the study can occur upon review of the safety data from all ongoing and previous subjects and with the concurrence of the study sponsor and the principal investigators.

In the event that attribution of causality of potential DLTs to study drug may be equivocal, discussions with the investigators, medical monitor and sponsor will occur and additional subjects may be enrolled at that dose level. Reviews will be conducted by the investigators, medical monitor and sponsor of all available safety data on an ongoing basis throughout the study. The study sponsor or its designee will notify the sites when enrollment into a dose level is complete and when the next dose level is open to enrollment during Stage 1.

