8.5 Describing Adverse Event Relationship to Study Drug and Study Procedures

The relationship of an adverse event to study drug should be assessed using clinical judgment, describing the event as either unrelated (no) or related (yes) consistent with the following definitions:

- **No:** Evidence exists that the adverse event had an etiology other than the study drug. For serious adverse events, an alternative causality must be provided (e.g., pre-existing condition, underlying disease, intercurrent illness, or concomitant medication).
- **Yes:** A temporal relationship exists between the adverse event onset and administration of the investigational medicinal product that cannot be readily explained by the subject's clinical state or concomitant therapies. Furthermore, the adverse event appears with some degree of certainty to be related to the study drug based on the known therapeutic and pharmacologic actions or adverse event profile of the investigational medicinal product. In case of cessation or reduction of the dose, the adverse event abates or resolves. In case of interruption and rechallenge, the event reappears upon rechallenge.

Of note, even in circumstances when the study drug is given intermittently or is interrupted temporarily before the onset of the adverse event, consideration should be given as to whether the study drug may have contributed to the event.

The relationship to protocol-mandated study procedures (e.g., procedures such as venipuncture or performance of an electrocardiogram) should be assessed using the following considerations:

- No: Evidence exists that the adverse event has an etiology other than the study procedure.
- Yes: The adverse event occurred as a result of a protocol-mandated procedure.

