9.2 Study Endpoints, Subsets, and Covariates

9.2.1 Study Endpoints

9.2.1.1 Primary Endpoints

- Incidence of adverse events and clinical laboratory abnormalities defined as dose-limiting toxicities (Stage 1)
- Progression free survival at 4.5 months (Stage 2)

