9.3 Sample Size Considerations

Approximately 9 subjects will be enrolled in Stage 1 of the study. Stage 1 is designed to determine the MTD up to a target dose of 250 mg/m²/day of RX-0201, thus the sample size for the study is not based on a formal statistical hypothesis but will be determined based on observed number of first-cycle DLTs at each dose level. The sequential 3+3 dose-escalation is

consistent with usual oncologic paradigms for dose ranging as the intent is to limit the number of subjects who are exposed to toxic doses of the treatment combination. The trial will use the standard National Cancer Institute (NCI) definition of MTD (starting dose associated with DLT in < 33.3% of subjects during the first cycle of therapy).

The planned sample size for Stage 2 is approximately 10 subjects in the everolimus arm and 20 subjects in the everolimus/ RX-0201 arm. The primary goal is to provide preliminary estimates of safety and efficacy endpoints when combining everolimus and RX-0201. Safety endpoints will be reported as described in Section 8. The primary efficacy endpoint is progression free survival estimated using the Kaplan-Meier method and associated 90% confidence intervals. Median PFS is expected to be 4.5 months in the everolimus only arm and 9 months in the combination arm. With 10 evaluable subjects in the everolimus only arm the width of the two-sided 90% confidence interval for 9-month PFS will be no more than ± 0.28 . With 20 evaluable subjects in the combination arm the width of the two-sided 90% confidence interval for 9-month PFS will be no more than ± 0.20 .

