## 5.5 Study Variables

### 5.5.1 Definition of Dose-Limiting Toxicity

Reference should be made to the CTCAE, Version 4.03 for grading of the severity of adverse events and laboratory abnormalities. Dose-limiting toxicities (DLT) will be evaluated during Cycle 1 of treatment. These DLTs will be graded and documented according the National Cancer Institute Common Terminology Criteria for Adverse Event (NCI CTCAE) (v4.03) A DLT will be defined as the occurrence of any of the following that are determined by the investigator to be related to RX-0201:

- Grade 4 neutropenia ( $ANC < 0.5 \times 10^9/L$ ) with fever or lasting 3 days or longer
- Any Grade 4 thrombocytopenia or Grade 3 thrombocytopenia associated with  $\geq$  Grade 1 hemorrhage
- Any  $\geq$  Grade 3 coagulation abnormality (defined by PT and/or INR and PTT values) associated with clinical hemorrhage  $\geq$  Grade 1.
- Nausea/vomiting  $\geq$  Grade 3 despite maximal antiemetic therapy; diarrhea  $\geq$  Grade 3 despite maximal anti-diarrheal therapy.
- Grade 4 thrombocytopenia (platelet count  $< 25 \times 10^9/L$ )
- Any other non-hematological toxicity  $\geq$  Grade 3 with the exception of alopecia

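### Stage 1 counts a DLT only if it is related to RX-0201 and leaves combination-attributed events unclassed, so the regimen's first-cycle DLT rate can be understated

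*Protocol*

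**What the plan says.** The Stage 1 objective (protocol 1.1) is the MTD of RX-0201, up to 250 mg/m²/day, given with everolimus. The primary endpoint (9.2.1.1) is the incidence of events defined as DLTs.

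- **Definition.** Protocol 6.5: "A DLT will be defined as any of the following adverse events that is considered by the investigator as related to RX-0201". SAP 5.5.1 likewise requires that the event be "determined by the investigator to be related to RX-0201".
- **Escalation.** Protocol 6.3: "If there are any dose limiting toxicities (DLTs) attributed to RX-0201 the following dose-escalation decisions will be followed".
- **Purpose of the 3+3.** Protocol 9.3: "the intent is to limit the number of subjects who are exposed to toxic doses of the treatment combination".
- **Attribution classes.** Protocol 6.7 and 6.8 distinguish events related to RX-0201, to everolimus and to the two together. Section 8.5 records only a yes or no relation to study drug. Its wording for a yes turns on whether another cause readily accounts for the event: "clinical state or concomitant therapies. Furthermore, the adverse event appears with some degree of certainty to be related to the study drug".
- **Early stoppers.** Under protocol 5.4, Stage 1 subjects who stop before completing Cycle 1 "for reasons other than the occurrence of a DLT may be replaced". SAP 7.2.4 limits the DLT set to subjects who have a DLT in the first 21 days or complete 2 weeks of RX-0201 in Cycle 1.
- **Result so far.** Protocol 2.3.2 reports 10 treated subjects (3, 4 and 3 at 125, 200 and 250 mg/m²/day). The common toxicities were attributed to the combination, and 81% of events were mild or moderate. It adds: "No significant events were attributed to RX-0201 alone". No DLT counts are given.

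**The concern.** The stated purpose of Stage 1 concerns the combination, but the counted endpoint concerns one of its two drugs. An event that meets a listed criterion and is put down to everolimus is not a DLT. For an event put down to the pair, the reader cannot tell whether it counts.

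This matters because attribution was hardest exactly where it was needed. Protocol 6.2 says no clinical data existed for the combination, and Stage 1 has no everolimus-alone group against which to check a judgement. The reported pattern, with the common toxicities assigned to the combination, makes the undefined class the important one.

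At stake is what the report can say about the tolerability of 250 mg/m²/day with everolimus, the dose taken into Stage 2 for up to 20 subjects. Without the uncounted events, a reader cannot separate a tolerable regimen from an effect of how events were attributed.

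**Working it through.** **The plan's own figures.** Three dose levels with 3 subjects each give 3 × 3 = 9, the planned Stage 1 size. The rule agrees with the MTD threshold of under 33.3%: 1/6 = 16.7% passes, while 2/6 = 33.33% does not. Protocol 9.3 gives no hypothesis, rate or power for Stage 1, so there is no stated operating characteristic to reproduce.

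**Pass probability.** Under 6.3 a dose passes with 0 of 3 DLTs, or with 1 of 3 followed by 0 of 3. With p the probability that a subject has a *counted* DLT:

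P(pass) = (1−p)³ + 3p(1−p)² × (1−p)³ = (1−p)³ + 3p(1−p)⁵

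This falls steadily as p rises. If the true rate of DLT-criterion events from all study treatment is π and a share c is counted, then p = cπ. Neither π nor c is in the documents; both are assumed here.

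At π = 40%:
- All counted, p = 0.40: 0.6³ + 1.2 × 0.6⁵ = 0.216 + 0.093 = 0.309
- Three quarters counted, p = 0.30: 0.7³ + 0.9 × 0.7⁵ = 0.343 + 0.151 = 0.494
- Half counted, p = 0.20: 0.8³ + 0.6 × 0.8⁵ = 0.512 + 0.197 = 0.709

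| Assumed true rate π | All counted | Three quarters | Half |
|---|---|---|---|
| 20% | 0.709 | 0.814 | 0.906 |
| 33.3% | 0.428 | 0.600 | 0.780 |
| 40% | 0.309 | 0.494 | 0.709 |
| 50% | 0.172 | 0.351 | 0.600 |

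Read the other way, a counted rate of 33.3% corresponds to a true rate of 0.333/0.75 = 44% if three quarters count, or 0.333/0.5 = 67% if half count. If every event counts, c = 1 and there is no effect.

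**Early stoppers.** Take a hypothetical cohort in which one subject stops in week 1 with an everolimus-attributed event that meets a criterion, and is replaced. With no other such events, the DLT set shows 0/3; all treated subjects show 1/4 = 25%. The 200 mg/m²/day cohort has 4 subjects. Replacement (5.4) or an added subject for equivocal attribution (6.3) could explain that, but the documents do not say which, if either.

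**What the planned outputs show.** The SAP's Safety Analyses text tabulates Cycle 1 DLTs by criterion and dose level, but only DLTs as defined. SAP 8.10 summarises all-cause events by severity, and SAP 8.11 lists Grade 3 and 4 events. Neither applies the 6.5 criteria, which also turn on duration, fever, bleeding or response to supportive therapy. So no planned output gives Cycle 1 DLT-criterion events by dose level regardless of attribution.

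**The case against.** The strongest reply has four parts.

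1. **The text does not exclude combination events.** It says related to RX-0201, not to RX-0201 alone, and an event related to both drugs is, on a plain reading, related to RX-0201. This stands. A reader might infer that combination-attributed events are not counted; the documents support only that their status is unclear, because 6.7 and 6.8 make them a separate class.

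2. **Section 8.5 need not tighten the filter.** A reader might infer that anything everolimus could explain becomes a no. But 8.5 defines a no as evidence of another cause, and 6.10 uses concomitant therapy for products other than those the protocol specifies, while 7.9 treats everolimus as one that it does specify. That inference is contestable and is not relied on here.

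3. **Other safeguards exist.** Escalation requires review of safety data from all subjects (6.3), the MTD rests on overall safety data (6.4), and a further review precedes Stage 2 (9.1.2). None is restricted to RX-0201-attributed events, so the discussion of equivocal cases is not the only protection. This stands too, but these reviews are unstructured and leave the counted endpoint as it is.

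4. **The objective is the MTD of RX-0201, with everolimus fixed at 10 mg.** Toxicity caused only by everolimus says little about the RX-0201 dose. If attribution is correct, leaving it out does not bias RX-0201's own contribution. It still understates what subjects on the regimen experience, which is the stated concern of 9.3.

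A further fair point is that Stage 1 is finished. Redefining the primary count now, with open-label results known, would contradict protocol 6.5 and be a post hoc change of endpoint.

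**Conclusion.** The point holds as a gap in definition and reporting. DLT-criterion events attributed to everolimus fall outside the Stage 1 primary endpoint, combination-attributed events have no defined status, and the replacement and analysis-set rules can remove affected subjects altogether. For the regimen, the resulting error can run only toward tolerability, because leaving out events can only raise the chance that a dose passes.

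Its size is unknown. The rise from 31% to 49% or 71% rests on an assumed true rate of 40% and assumed counted shares of three quarters and half. If combination events were in fact counted and few events were put down to everolimus alone, the effect may be close to nil.

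A reader might go further and infer that the MTD is biased upward, or that 250 mg/m²/day passed only because of the filter. The documents do not support this: they give no DLT counts and no attribution of individual events, the dose was capped at 250 mg/m²/day, and the decision drew on all safety data. Nor does the point reach every Grade 3 or 4 event, since some Grade 3 haematological events are not DLTs whatever their cause.

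**What to change.** Keep the protocol-defined DLT count as the primary tabulation. In SAP 8.7 and the Safety Analyses text, add one table by dose level of all Cycle 1 events that meet a criterion in protocol 6.5, whatever their attribution. Cover every treated Stage 1 subject, including any who were replaced or are not DLT-evaluable. Split the table by attribution: RX-0201, everolimus, combination, or another documented cause. Present it beside the primary count wherever the report states an MTD or describes the tolerability of the combination.

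Reconcile protocol 6.5, 6.7, 6.8, 8.5 and 9.3 on how combination-attributed events are classed, and state in the report how they were classed in Stage 1.

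The cost is one table, a re-review of Cycle 1 adverse events in 10 subjects, and a reported toxicity rate that may look less favourable. No completed escalation decision changes; the gain lies in what can be concluded about the regimen.

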6.6 RX-0201 Dosage Modifications

Whenever possible, dose modifications of study drug should be discussed between the investigator, medical monitor, and the sponsor prior to implementation. The appropriate clinic staff should administer the new dose level and inform the subject about the change in dose level.

6.6.1 RX-0201 Dose Modifications During a Cycle

If a subject experiences a RX-0201-related DLT (as defined in Section 6.5), SAE, or other intolerable adverse event and requires a dose reduction, RX-0201 administration should be interrupted, as necessary, until the adverse event resolves or stabilizes to an acceptable degree (generally to the pretreatment severity grade). If appropriate, more frequent laboratory monitoring may be instituted until abnormalities have recovered to the pretreatment severities. Thereafter, RX-0201 may be reinstated, but the dose of RX-0201 for the remainder of that cycle should be reduced by 1 dose level. Successive adjustments to progressively lower dose levels can be made. If the subject cannot tolerate RX-0201 at Dose Level 1 (125 mg/m²/day) then the subject should be discontinued from RX-0201 therapy.

6.6.2 RX-0201 Dose Modifications at the Beginning of the Next Cycle

A new cycle of RX-0201 treatment may begin no earlier than Day 1 of the new cycle but should be delayed, as necessary, until adverse events or laboratory abnormalities have returned to baseline levels. If adverse events or laboratory abnormalities are not resolved to baseline, week-by-week delays in initiating the new cycle of treatment should be instituted. Once all toxicities have returned to baseline, the next cycle of therapy can be initiated.

Subjects experiencing any of the DLTs described in Section 6.5 in the current cycle of therapy should have the dose in the next cycle of therapy reduced by 1 dose level. Subjects who required an intra-cycle dose reduction, during the current cycle of therapy, should have the dose in the next cycle of therapy administered at no higher than the highest dose tolerated in the current cycle. Successive inter-cycle adjustments to progressively lower dose levels can be made. If the subject cannot tolerate RX-0201 at Dose Level 1 (125 mg/m²/day) then the subject should be discontinued from RX-0201 therapy.

Subjects in Stage 1 will receive additional cycles at the same dose to which they were assigned in Cycle 1.

6.6.3 RX-0201 Dose Re-Escalation

After a dose is reduced, the dose need not be re-escalated, even if there is minimal or no toxicity with the reduced dose. However, if the subject tolerates a reduced dose of RX-0201 for ≥ 3 weeks then the RX-0201 dose may be increased to the next higher dose level, at the discretion of the investigator. Such re-escalation may be particularly warranted if further evaluation reveals that the adverse event that led to the dose reduction was not RX-0201-related. Successive adjustments to progressively higher dose levels can be made at 3-week intervals.

6.6.4 RX-0201 Dose Escalation (Stage 1 only)

Subjects receiving a dose of RX-0201 in Stage 1 that is less than the MTD or target dose and for whom the principal investigator feels are receiving benefit, may receive an increased dose following discussions with the Sponsor.

6.6.5 Everolimus Adjustments, and Modifications

Dose adjustments for everolimus will be allowed for adverse events according to the approved package insert or best clinical practices. See everolimus package insert for full details regarding dose adjustment.

6.7 Everolimus Dose Delays

Dose delays for everolimus will be allowed according to the approved package insert or best clinical practices. If the start of a cycle (i.e., day 1 of a cycle) is delayed due to everolimus related toxicity, then RX-0201 dosing may continue on schedule.

If an adverse event occurs that is related to RX-0201, everolimus may continue on schedule.

If an adverse event occurs that is related to the combination of RX-0201 and everolimus, dosing of both drugs may be delayed until the event is resolved.

6.8 RX-0201 Dose Delays

If the start of a cycle (i.e., day 1 of a cycle) is delayed due to RX-0201 related toxicity, then everolimus dosing may continue on schedule.

If an adverse event occurs that is related to the combination of RX-0201 and everolimus, dosing of both drugs may be delayed until the event is resolved.

